8 ANALYSIS SETS

The main population for non-safety analysis will be the As Exposed Set. Safety will be analyzed using the Safety Set.

As this study was intended to investigate the effects of IQOS and/or cigarettes on periodontitis treatment, therefore patients who are not in the cigarette, IQOS or dual-user product use categories will not be analyzed except in the Safety Set described below. There is no systematic way to quantify product use for patients who were using other products and the effects of these products on periodontitis are not known. Furthermore, this study was not powered to assess the impact of other products on periodontitis.

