### 12.3 Product use

[figure not shown]
Although patients are being requested to use solely the product allocated to their respective study arm, it is considered that not all patients randomized to the IQOS arm or to continue smoking cigarettes will exclusively use the randomized product at all times during the study. Patients may concomitantly use IQOS and cigarettes (dual-use). To assess dual use of IQOS and cigarettes, PMI has defined categories of pattern of product use.

Product use pattern categories will be specified based on the average number of product used per month of each category (i.e., Marlboro HeatSticks or smoked cigarettes) as self-reported in the product use questionnaire over the study duration. Further determinants, such as percentages of the respective products, or numbers of other nicotine-containing products may be used, and will be provided in the SAP.

Actual product use pattern categorization is described in Figure 3. Primary analysis will consider only those patients who used only HeatSticks and/or cigarettes. Those who used other nicotine-containing products (e.g., e-cigarettes) will be considered in a separate category, "Other" (not represented in Figure 3). More granular product exposure categories may be used for the detailed description of the product use patterns observed in the study. Full details of the product use categories will be reported in the SAP.

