### 12.4.2 Full Analysis Set (FAS)

The Full Analysis Set (FAS) consists of all randomized patients who have at least one post-randomization product use experience, and who have at least one valid non-safety assessment after randomization. The FAS will be analyzed by randomized study product.

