## 12.6 Primary Analysis

The primary analysis evaluates the change from baseline in PD, which will be calculated for each patient across all sites with a baseline PD  $\geq 4$  mm, resulting in one value per patient per endpoint for each visit (baseline, Month 3 and 6).

The primary analysis will be performed on the As Exposed Set using a mixed model for repeated measurements (MMRM) for only subjects who have used cigarettes and/or Heatsticks. The model will include the PD change from baseline as the dependent variable, adjusting for daily cigarette consumption and disease severity at V1, full mouth PD at V1, exposure group and its interaction with visit. Site will be included as a random effect. The modeling assumptions will be evaluated and the model fit will be assessed by the analysis of the residual (diagnostics) and by comparing the values predicted vs. the observed values (calibration).

Additionally, the analysis will be performed on the FAS, PP and Adherent Use populations as a supportive sensitivity analysis. Additional sub group analyses such as for “Other” product use groups may be analyzed and will be defined in the SAP.

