5.2 Product Use

The number of Cigarettes, Heatsticks, and other nicotine/tobacco containing product used daily, as reported by the patient and collected in the electronic diary, will be used to monitor product use and evaluate adherence to product allocation.

Patients will be classified according to their monthly actual product use pattern into four categories: cigarette users; IQOS user, dual user, or other as described in Figure 2. “Other” will include the following products: Other heat not burn products, e-cigarettes, Smokeless Tobacco Pipe, Smokeless Tobacco, Cigars/Pipes/Kiseru/Shisha, and Nicotine Replacement Therapy.

The calculation of the monthly product use to classify patients into the four categories is described in section 5.2.3

Confidentiality Statement

Data and information contained in this document are considered to constitute trade secrets and confidential commercial information, and the legal protections provided to such trade secrets and confidential information are hereby claimed under the provisions of applicable law. No part of this document may be publicly disclosed without the written consent of Philip Morris Products S.A

[figure not shown]

Figure 2: Product Use Categories

Abbreviations: HS, Marlboro HeatSticks; cig, cigarette

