7 CHANGES FROM THE PROTOCOL SPECIFIED STATISTICAL ANALYSES

Changes to “As Exposed Set” to exclude patients with major protocol deviations that affect evaluability of the data. The removal of the “Adherent Use Set” from the analysis sets.

Confidentiality Statement

Data and information contained in this document are considered to constitute trade secrets and confidential commercial information, and the legal protections provided to such trade secrets and confidential information are hereby claimed under the provisions of applicable law. No part of this document may be publicly disclosed without the written consent of Philip Morris Products S.A.

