8.2 Full Analysis Set

The Full Analysis Set (FAS) consists of all randomized patients who have at least one post-randomization product use experience, and who have at least one valid non-safety assessment after randomization. The FAS will be analysed by randomized study product.

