8.3 Per Protocol Set

The Per Protocol Set (PP) is the subset of the FAS who fulfill key compliance criteria of the protocol and have no major protocol deviation that influences the evaluability of the study data. The major protocol deviations are described in “12.1 Major Protocol Deviations”. The Per Protocol will be analyzed by randomized study product.

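### The supportive FAS and PP analyses have no assigned-arm model, and SAP 8 drops users of other products from the FAS after randomisation

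*SAP*

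**What the plan says.** **Who is analysed.** SAP 8 opens with a rule over all the sets: "patients who are not in the cigarette, IQOS or dual-user product use categories will not be analyzed except in the Safety Set described below". SAP 5.2 assigns patients to four categories from self-reported use after randomisation. The Other category ranges from non-IQOS heated products to "Cigars/Pipes/Kiseru/Shisha, and Nicotine Replacement Therapy". SAP 8.2 and protocol 12.4.2 define the FAS as every randomised patient with some product use and a valid non-safety assessment after randomisation, with no condition on product type. SAP 7 lists two changes from the protocol: altering the As Exposed Set "to exclude patients with major protocol deviations that affect evaluability of the data", and removing the Adherent Use Set. It does not mention Other users.

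In the protocol, section 12.3 ties the restriction to the primary analysis: "Primary analysis will consider only those patients who used only HeatSticks and/or cigarettes". Section 12.6 repeats it for the primary model and then adds: "Additionally, the analysis will be performed on the FAS, PP and Adherent Use populations as a supportive sensitivity analysis".

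**How the sets are grouped.** SAP 8.2: "The FAS will be analysed by randomized study product". Protocol 12.4.2: "The FAS will be analyzed by randomized study product". SAP 8.3: "The Per Protocol will be analyzed by randomized study product". SAP 9.1.3.1 gives descriptive statistics by randomisation arm for sets other than As Exposed and Safety.

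**Which model.** For PD in the FAS and PP, the contents and sample-code rows in SAP 9.5.1.2 only point to the primary analysis. SAP 9.5.2.2 does the same for PD at 3 months and CAL, and sends the biomarkers to the As Exposed biomarker model.

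**The concern.** The primary analysis compares groups formed by behaviour after randomisation. The FAS is where the plan keeps the randomised comparison, so a reader will look there to see whether the As Exposed result could be self-selection. That check works only if the FAS keeps eligible patients whatever they used and estimates the effect of assignment.

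On the text, neither condition is secure. The exclusion rests on a post-randomisation variable, and the patients concerned are foreseeable. Patients are advised to quit at every visit, those who try are referred for support, and quitters stay in the study. Someone who follows that advice using nicotine replacement can be classed as Other and leave the FAS analysis.

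The model is the second problem. If product use stays in it, the FAS run compares behaviour groups again. If arm is swapped in but average daily cigarette use at each visit stays, the arm effect is adjusted for something that assignment is meant to change.

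**Working it through.** **1. The plan's own figure.** Inputs from protocol 12.2 and SAP 6: difference 0.25 mm, SD 0.5 mm, one-sided alpha 0.025, power 80%, 15% dropout plus 10% non-adherence.

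- Normal approximation: n = 2 × (1.960 + 0.842)² × 0.5² / 0.25² = 62.8, so 63 per arm. The t-test gives 63.8, so 64 per arm.
- 64 / 0.75 = 85.3, so 86 per arm and 172 in total.

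The stated sample size reproduces. The defect is in the specification, not the arithmetic.

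**2. Population, passages side by side.** SAP 8 bars Other users from everything but the Safety Set. SAP 8.2 and protocol 12.4.2 admit them to the FAS. Both cannot be followed. SAP 9.5.1.1 already limits the primary model to IQOS, cigarette and dual users, so the primary analysis does not need the SAP 8 rule. The reason given in SAP 8 (other use cannot be quantified and its effects are unknown) concerns exposure grouping. A by-arm analysis does not need use to be quantified.

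The share of Other users is not given. At assumed shares of 2%, 5% and 10%, the rule removes 172 × 0.02 = 3.4, 172 × 0.05 = 8.6 and 172 × 0.10 = 17.2 patients.

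**3. Model, passages side by side.** The primary model in SAP 9.5.1.1 lists 13 covariates. They include product use pattern, its interactions with visit and two baseline factors, and average daily cigarette use at each visit (covariate 7, defined in SAP 5.2.5 as use since randomisation). Assigned arm is not listed. The reported contrasts are cigarette user against IQOS user and dual user. The schematic code requests LS means by product use and visit; its `trt01a` term is not defined in the SAP and is absent from the CLASS statement. The biomarker model in SAP 9.5.2.1 has the same structure. SAP 9.5.2.2, written for the FAS and PP, words most of its tests as comparisons of user categories, with one looser reference to CC and IQOS.

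Whether covariate 7 can be dropped is unclear: SAP 9.5.1.1 says covariates 8-12 are assessed, then names 7-14, in a list that ends at 13.

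**4. Illustration of keeping covariate 7.** Assumed inputs:

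- 73 evaluable per arm (86 × 0.85 = 73.1), SD 0.5 mm, and a 0.25 mm benefit in actual switchers.
- Cigarettes per day at V1: mean 17, SD 4 or 7, floor 10. Actual IQOS users smoke none.
- Non-adherence (IQOS arm/cigarette arm): 10/10, 10/0, 20/5 and 5/5%.
- 6,000 simulated trials per setting, one post-baseline visit, and a linear model with arm and V1 cigarettes per day. This simplifies the planned repeated-measures model.

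Expected by-arm difference = 0.25 × (1 − non-adherence in IQOS arm − non-adherence in cigarette arm), giving 0.20, 0.225, 0.1875 and 0.225 mm.

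| Model | Arm estimate (mm) | SE (mm) |
|---|---|---|
| Without covariate 7 | 0.188 to 0.228 | 0.083 to 0.084 |
| With it, benefit proportional to cigarettes avoided | −0.001 to 0.004 | 0.121 to 0.183 (both cases) |
| With it, benefit from switching only | 0.020 to 0.094 | as above |

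If covariate 7 is instead treated as droppable at p > 0.05, it was dropped in about 40 to 82% of trials and the mean arm estimate was about 0.05 to 0.18 mm. Attenuation is smaller but remains.

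**5. Cost of a by-arm estimate.** With 10% full crossover in each arm, 0.25 × (1 − 0.10 − 0.10) = 0.20 mm. At 73 per arm, nominal t-test power is 85.1% at 0.25 mm and 67.0% at 0.20 mm. If the non-adherent 10% merely contribute no effect, the difference is 0.25 × 0.90 = 0.225 mm and power is 77.1%.

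**The case against.** The best reply is that the grouping is already stated. SAP 8.2 and 8.3 say by randomised product, and the descriptive tables for these sets go by arm. The cross-reference would then mean the same method with arm in place of product use. That is a fair guess at intent, but it is not written, and the user-category tests in SAP 9.5.2.2 point the other way. It also leaves covariate 7 in the model.

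On the population, SAP 8 can be read as an overarching rule with a stated reason. Protocol 12.6 can be read as carrying the primary restriction into the FAS, in which case SAP 7 had nothing to declare. Section 12.6 does allow either reading, so the passages need reconciling. The clash between SAP 8 and the FAS definitions remains.

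Three further points stand in part:

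- Excluding Other users from PP is not evidently inconsistent, because PP requires compliance. For PP the case rests on the model alone.
- The simulated 0.00 to 0.09 mm applies only if covariate 7 is retained, and the zero result follows from assuming benefit proportional to cigarettes avoided.
- Returning to the protocol covariates also drops baseline tooth mobility, time since last SRP and the extraction counts, so the FAS and As Exposed models would differ in more than grouping.

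**Conclusion.** The concern holds and should be fixed. It is certain that SAP 8 conflicts with the FAS definitions and that the models to which the FAS and PP are sent list no assigned-arm term. What the authors meant by the cross-reference is less certain. Followed literally, the plan produces no by-arm estimate in all eligible randomised patients to set beside the As Exposed result.

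The effect of the exclusion cannot be sized, because the documents give neither the frequency nor the response of Other users. Figure 2 is not shown, so the category boundaries cannot be checked. The model effect is an illustration on assumed inputs: if arm is substituted and covariate 7 retained, the FAS would understate the effect of assignment. These analyses are supportive, so the primary As Exposed estimate and test, the testing hierarchy and the sample size do not change.

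**What to change.** 1. Limit the SAP 8 exclusion to the As Exposed analyses, so that the FAS keeps every patient who meets SAP 8.2 and protocol 12.4.2 whatever product was used. Otherwise, declare the restriction in SAP 7 and reconcile it with protocol 12.3 and 12.6.
2. Write out the FAS/PP model for PD and CAL as the protocol 12.6 model with assigned arm in place of exposure group: arm, visit, arm by visit, V1 daily cigarette consumption, V1 severity, V1 full-mouth PD (full-mouth CAL for CAL), and site as a random effect. Include no product use or cigarette use measured after randomisation.
3. Make the same substitution in the biomarker model, with the protocol 12.7 baseline covariates: daily cigarette consumption, sex and baseline biomarker level.
4. Reword the FAS/PP tests in SAP 9.5.2.2 as comparisons of assigned arms.
5. Report the FAS estimate and 95% CI beside the As Exposed result.

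The cost is SAP wording and one written-out model per endpoint type. No new data are needed, and the protocol's FAS definition and primary analysis stay as they are. The by-arm estimate will be diluted by crossover, as shown above, but only in a supportive analysis.

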8.1 As Exposed Set

The As Exposed Set consists of all randomized patients who have at least one post-randomization product use experience, who have at least one valid non-safety assessment after randomization and have no major protocol deviation that influences the evaluability of the study data. The major protocol deviations are described in “12.1 Major Protocol Deviations”. The As Exposed Set will be analysed by actual exposure (see “product use pattern”).

8.2 Full Analysis Set

The Full Analysis Set (FAS) consists of all randomized patients who have at least one post-randomization product use experience, and who have at least one valid non-safety assessment after randomization. The FAS will be analysed by randomized study product.

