### 6.5.4 Adherence to Investigational Product(s)

Adherence to the allocated product will be monitored using a questionnaire on self-reported current tobacco and nicotine containing tobacco product consumption (including frequency and quantity of product use) over the past month (section 7.5.7).

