4.3.3 Compliance to Product Allocation

Patients will be allowed to use their allocated products (cigarette or IQOS) according to their needs. However, from Visit 2 onwards, information on the risks of the use of tobacco containing products and advice to quit smoking will be given to patients at every visit. The patients who quit smoking or using IQOS or those who quit smoking and start using IQOS will not be discontinued from the study, will receive their financial compensation and will come at all scheduled visits for assessments.

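### The FAS, the broadest set analysed by randomised arm, depends on product use after randomisation, so complete quitters and users of other products can be dropped from the by-arm comparison although their PD is measured

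*SAP*

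**What the plan says.** **Entry to the FAS.** SAP 8.2 opens: "The Full Analysis Set (FAS) consists of all randomized patients who have at least one post-randomization product use experience". In full, the condition is "at least one post-randomization product use experience, and who have at least one valid non-safety assessment after randomization". Protocol 12.4.2 agrees: the set "consists of all randomized patients who have at least one post-randomization product use experience". Neither document says whether the product must be the allocated one or may be any tobacco or nicotine product.

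**Grouping.** SAP 8.2: "The FAS will be analysed by randomized study product". SAP 8.3 defines the Per Protocol Set as a subset of the FAS and groups it the same way: "The Per Protocol will be analyzed by randomized study product". The lead analysis is different: "The main population for non-safety analysis will be the As Exposed Set", and that set is grouped by actual product use (SAP 8.1).

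**A second condition.** The introduction to SAP section 8 confines patients outside the cigarette, IQOS and dual-user categories to the Safety Set. SAP 8.2 does not repeat this. Protocol 12.4.2 does not contain it, and SAP section 7 does not list it as a change from the protocol. SAP 5.2 names four categories: those three plus other, which is defined by use of other products. The text names no category for no use at all.

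**Follow-up of quitters.** SAP 4.3.3: "The patients who quit smoking or using IQOS or those who quit smoking and start using IQOS will not be discontinued from the study". They attend all scheduled visits, so PD is examined at V3 and V4.

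**Role of the FAS.** SAP 9.5.1.2 and protocol 12.6 make it a supportive or sensitivity analysis of the primary endpoint.

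**The concern.** The main comparison groups patients by what they chose to use, so it carries self-selection. The by-arm analyses are the check on that, and their value is that membership does not depend on anything that happens after allocation. In an open-label trial, whether a patient uses tobacco after learning the arm is such an event. Protocol 7.2 has cessation advice given at every visit and encourages any attempt to quit, so complete quitters are foreseeable. The plan collects their primary-endpoint data and may then set them aside in the one analysis where randomisation should protect the estimate. The same applies to patients who take up other products.

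At stake is the credibility of the by-arm check and the loss of PD data already collected. The primary test and the sample size are not at stake.

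**Working it through.** **1. The plan's own figures.** Protocol 12.2 gives a difference of 0.25 mm, SD 0.5 mm, one-sided alpha 2.5%, power 80% and 25% for dropout plus switching.
- Normal approximation: n = 2(1.960 + 0.842)² × 0.5² / 0.25² = 62.8, so 63 per arm.
- Two-sample t-test: 63.77, so 64 per arm, as stated.
- 64 / 0.75 = 85.3, so 86 per arm and 172 in total, as stated.

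These reproduce. The point concerns who is counted, not N.

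**2. Who can be left out.** All these patients have PD at V3 and V4 if they attend.

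| Patient | Product-use condition in SAP 8.2 | Category rule in SAP section 8 |
|---|---|---|
| Stops all tobacco at V2, randomisation taken as at V2 | Not met | No named category fits |
| Stops all tobacco at V2, randomisation taken as after V1 | May be met by cigarettes smoked before V2 | No named category fits if reported use is zero |
| Quits some weeks later | Met | Depends on Figure 2, because SAP 5.2.2 and 5.2.3 average use since randomisation |
| Classed as other | Met if any product counts | Excluded |

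Two things cannot be settled from the text. Figure 2 is not shown in the copy available, so how zero use is classified cannot be confirmed. The time of randomisation also differs between places: SAP 4.3.1 and protocol 6.3 put it after the V1 assessments with the arm disclosed at V2, while protocol 6.2.1, Table 4 and Appendix 1 put it at V2. The two visits are 7 to 14 days apart, and smoking is allowed in between.

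**3. Shift in the by-arm difference.** Inputs: the 0.25 mm effect and the assumption in protocol 12.2 that the IQOS arm responds like former smokers. The documents give no quit rate, so the fraction q is an assumption, taken as 2% to 10% of one arm of 86.

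*Quitters in the cigarette arm*, each assumed to gain the full 0.25 mm:
- difference with them kept = 0.25(1 − q)
- difference with them left out = 0.25
- overstatement = 0.25q

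| q | Patients (86q) | Difference if kept (mm) | Overstatement (mm) |
|---|---|---|---|
| 2% | 1.7 | 0.245 | 0.005 |
| 5% | 4.3 | 0.2375 | 0.0125 |
| 10% | 8.6 | 0.225 | 0.025 |

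*Quitters in the IQOS arm*: if the whole arm already responds like former smokers, a quitter has the same expected response as the others, so leaving quitters out shifts the difference by about 0.

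For scale, the design standard error is 0.5 × √(2/64) = 0.088 mm, so 0.005 to 0.025 mm is about 0.06 to 0.28 of a standard error.

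**4. Loss of precision.** If one arm loses fraction q, the standard error is multiplied by √{[1/(1 − q) + 1]/2}: 1.005 at 2%, 1.013 at 5% and 1.027 at 10%. That is about 0.5% to 2.7%.

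No comparable figure can be given for other users, because the documents state no assumption about their number or response.

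**The case against.** The strongest reply is that the rule will rarely bite. Only patients who do not intend to quit are eligible. One use is enough. The IQOS arm is handed HeatSticks in the starter kit at V2. If randomisation follows the V1 assessments, nearly everyone has smoked after randomisation before learning the arm. All of this stands as regards the sentence in SAP 8.2. It does not answer the category rule in section 8, which looks at use over the study rather than at a single experience.

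Several stronger readings are tempting and are not supported:

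- *That the FAS is the only by-arm set.* The Per Protocol Set is also by arm. As a subset of the FAS, it cannot bring an excluded patient back.
- *That stopping at V2 certainly removes a patient.* This depends on the unresolved time of randomisation and on an undefined product use experience.
- *That the rule acts on the IQOS arm alone.* Cessation advice goes to all patients, and a cigarette-arm quitter is equally exposed. Which arm would lose more is unknown.
- *That patients without returned questionnaires cannot qualify.* Protocol 6.5.4 says "Adherence to the allocated product will be monitored using a questionnaire on self-reported current tobacco and nicotine containing tobacco product consumption", but that concerns adherence. The FAS text does not make the questionnaire the proof of use, and urinary nicotine equivalents are measured at V3 and V4.

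It can also be said that a wider FAS would not by itself give a clean by-arm comparison, because SAP 9.5.1.2 refers back to a primary model that contains product-use pattern and on-study cigarette use. That is correct. It is a separate matter of model specification and does not justify the entry condition.

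**Conclusion.** The point holds in a limited form. As written, the by-arm set depends on product use after randomisation through two rules, and following them can discard PD data from patients whom the plan deliberately keeps under observation. The firmer of the two is the exclusion in SAP section 8, which on its wording also reaches other users. The condition in SAP 8.2 and protocol 12.4.2 adds to it, with an effect that depends on when randomisation is taken to occur.

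The likely size is small: an overstatement of 0.005 to 0.025 mm, or 2% to 10% of the 0.25 mm design effect, with a one-arm standard error inflation of about 0.5% to 2.7%. This rests on an assumed 2% to 10% quitting in the cigarette arm and on those patients gaining the full former-smoker benefit. A reader might apply the same shift to IQOS-arm quitters, but under the plan's own assumption theirs is about 0. Because the FAS analysis is supportive, the formal conclusion of the trial does not turn on this. It should still be corrected, because a by-arm check ought not to depend on the behaviour it is there to guard against.

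**What to change.** 1. In SAP 8.2 and protocol 12.4.2, define the FAS as all randomised patients with a V1 and at least one post-randomisation periodontal examination, analysed by randomised arm irrespective of product use.
2. In the introduction to SAP section 8, state that the exclusion of patients outside the cigarette, IQOS and dual-user categories does not apply to the FAS.
3. Keep the product-use conditions for the As Exposed Set.
4. Reconcile the time of randomisation across SAP 4.3.1, protocol 6.2.1 and 6.3, Table 4 and Appendix 1.

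No new data are needed and N stays at 172. The cost is a short SAP edit, which SAP section 1 allows up to finalisation before database lock, plus a matching written protocol amendment submitted to the IRB under protocol 1.1.
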